6.5. Measures to Minimize Bias

6.5.1. Randomization

At screening, subjects will be assigned a subject identification number. When a subject is confirmed to be eligible for the clinical study, the subject will be randomized. Allocation of each subject to a given treatment will be done using a centralized electronic system (interactive voice/web response system [IXRS]). IP will be randomized in a 2:1 ratio to GLPG3970 or placebo.

6.5.2. Blinding and Unblinding

This is a randomized, double-blind clinical study. The subjects and the entire clinical study team, including the investigators, clinical study coordinators, and sponsor personnel are blinded to treatment assignment.

Blinded and packaged medication will be provided to the site. All IP formulations will be identical in appearance, shape, smell and taste and will be packaged in the proper proportion to assure desired dosages and maintenance of the blinding.

The blind can be broken by the investigator for the safety of a subject. The investigator is encouraged to discuss considerations to break the blind with the medical leader, whenever possible and where the situation allows. However, the responsibility to break the treatment code in emergency situations resides solely with the investigator. The investigator is not required to discuss unblinding beforehand if he or she feels rapid emergency unblinding is necessary, but is required to inform the sponsor in within 24 hours after unblinded has occurred.

The blind can be broken by the investigator via IXRS by the investigator.

If the blind is broken for any reason during the course of the clinical study, the moment on which the blind was broken and all other relevant information will be documented by the study site. The reason for breaking the blind will be indicated and justified in the source documentation.

If an AE leads to unblinding, the AE will be given as the reason for unblinding. All subjects who are unblinded should, where possible, complete the follow-up visit assessments 14 ± 3 days after unblinding. Any AEs will be followed until resolution.

The code-break information (via IXRS vendor) will be provided to the bioanalytical laboratory responsible for PK sample analysis, the person responsible for providing unblinded data to the data safety monitoring committee, to the pharmacovigilance vendor for SAE reporting purposes, and, if applicable, to the contract research organization (CRO) performing population PK/PD analyses.

7. INVESTIGATIONAL MEDICINAL PRODUCT

7.1. Identity of the Investigational Medicinal Product

IP will be supplied to the pharmacist of the site, by and under the responsibility of the sponsor, who will also provide the investigator and pharmacist (or appropriate qualified member of the clinical study staff) with appropriate certificates of analytical conformity and European Union (EU) Qualified Person release documents.

For more details on the composition of the IP, refer to the latest version of the IB and its relevant updates/addenda.

Detailed instructions on preparing and storing the IP will be provided to both the study site and the subjects.

7.2. Dosage and Administration

GLPG3970 will be provided as a powder and solvent for oral solution, to be reconstituted prior to use. The final dosage form for administration is an oral solution containing 400 mg of the active pharmaceutical ingredient G1567970 (G1567970 is the compound code for GLPG3970). A placebo powder and solvent for oral solution, to be reconstituted prior to use, will also be provided.

The IP needs to be taken once daily at approximately the same time every morning and on an empty stomach (i.e. IP intake should be at least 1 hour prior and at least 2 hours after food intake). At baseline (Visit 1), Day 15 (Visit 3), and Day 43 (Visit 5), and if applicable the ED visit, subjects need to come for the study visits in a fasting state (no food intake for at least 8 hours).

Subjects will receive powder and solvent to take home. The total content of the oral solution, reconstituted from the whole amount of powder and solvent, will need to be drunk. Detailed instructions for preparing and storing the applicable doses will be provided to the subject via on-site training on dummy kits and via a patient leaflet.

If a subject misses a dose (e.g. because he/she forgot to take the medication), he/she should take the missed dose within 12 hours after the planned intake time. If IP is not taken within 12 hours after the planned time, the missed dose should be skipped. For each dose taken at home, the time and date should be recorded in the subject's diary card.

7.3. Packaging, Labeling and Distribution

IP packages will be labeled with clinical study-specific details, including storage conditions.

All manufacturing, packaging, and labeling operations will be performed according to Good Manufacturing Practice for Medicinal Products and the relevant regulatory requirements.

Each medication kit will be identified with a unique kit number. Multiple kits can be provided to a subject at each visit, providing the subject with sufficient IP to cover the period until the next scheduled visit.

The distribution of IP to the site will only occur after the required local documentation is obtained, including clinical study approval by regulatory authorities and the IECs/IRBs, documentation on which the assessment of the investigator's qualifications was based (e.g. curriculum vitae), and the signed and dated study agreement and financial agreement.

To ensure study subjects maintain dosing per protocol requirements during this study special delivery services through DTP shipments of IP from the investigational site to the subject can be implemented in case of SARS-CoV-2 restrictions. DTP should only be used in case of emergency where on-site IP dispensation is not possible, and if allowed per local regulations. Local guidelines must be followed and regulatory approval or notification of authorities may be required. Agreement of the subject to receive IP at home is required prior to the shipment of IP from the investigational site to the subject's home. The DTP process used will be reviewed and approved by the sponsor, but the DTP shipments will be coordinated by the investigational site(s) in collaboration with the local CRO without the involvement of the sponsor to ensure clinical study integrity in case of SARS-CoV-2 restrictions.

7.4. Storage

Sites are to store IP supplies in a secure area until dispensed. Powder and solvent for oral solution are to be stored at room temperature (below 30 °C), should not be refrigerated or frozen and protected from light. Both the study sites and subjects will receive additional information on preparation and storage of the IP.

Sites will be required to monitor the storage temperature by using at least a min-max temperature-recording device and to keep a minimum to maximum temperature log, which must be completed each working day in order to establish a record of compliance with these storage conditions.

The investigator will instruct subjects on how the IP should be stored at home. Storage conditions to be taken into account by the subject when taking IP home, are described in the patient leaflet.

7.5. Treatment Compliance and Drug Accountability

The investigator should discuss treatment compliance with the subject prior to the start of the study. Missed doses should be discussed to try to ascertain the reason(s). Every effort should be made to ensure the proper subject dose. Subjects with poor compliance will be retrained by the

site. Subjects will record IP administration (amount administered, date and time of IP administration) done at home in a subject diary. On Visit Day 1, Day 15 ± 2 , Day 29 ± 2 and Day 43 ± 2 administration of IP must occur at the site and will be captured in the eCRF.

The pharmacist or designated clinical study staff will maintain a log (paper or electronic) of the total amount of IP received at site, amount dispensed to the subject, and number of empty and full bottles returned to the site. IP supplies for each subject will be inventoried and accounted for throughout the clinical study. At the end of the treatment period, these records will be checked against the inventory by the study monitor. All clinical supplies will be stored in locked facilities.

Subjects will return any unused IP and empty IP packages at each study visit and/or ED Visit. Upon sponsor approval, all used and unused IP are to be returned from the sites and/or any vendor involved in the clinical study supplies management activities to the agreed location (depot), if possible. All returns and destructions must be properly documented.

8. CLINICAL STUDY ASSESSMENTS

Every effort should be made to ensure that CSP-required tests and procedures are completed as described in the Schedule of Activities (see Section 8.11). To avoid inter-observer variability, every effort should be made to ensure that all safety and efficacy evaluations are completed by the same individual who made the initial baseline determinations. In case study assessments are not performed for reasons related to SARS-CoV-2 pandemic restrictions, this should be documented in the medical records and subject's e-CRF.

In case a randomized subject is not available to attend a scheduled study visit on site due to SARS-CoV-2 travel restrictions, a phone call or a televisit may be conducted instead. It is strongly recommended to conduct planned study assessments for the applicable visit as per protocol as much as possible. If possible and if local regulations allow and the subject agrees, trained study staff or trained personnel are encouraged to collect study assessments at the study subjects' home or a local facility if social distancing and hygiene rules can be applied.

Only staff trained in conducting the protocol planned assessments are authorized to perform home or local facility visit assessments and the alternative arrangements need to be adequately documented. Direct to patient shipments are possible if needed. Subjects presenting with signs and symptoms of infection, including SARS-CoV-2 infection should immediately contact the site investigator, who should inform the sponsor's medical responsible as soon as possible, and SARS-CoV-2 testing should be performed.

8.1. Timing of Assessments

The study assessments described below will be performed at time points as specified in the Schedule of Activities in Section 8.11. A window of ± 2 days is allowed for Visits 2, 3, 4, and 5; and a window of ± 3 days is allowed for the Follow-up Visit.

ICF needs to be signed before any study procedure, including screening procedure, is carried out.

The sequence of study assessments during the treatment period(s) will be as follows when planned at the same time point:

1. [REDACTED]
2. 12-Lead ECG and vital signs.
3. Blood sampling for clinical laboratory assessments and PK.
4. [REDACTED]

Note 1: In case of blood sampling via catheter, the order of predose assessments versus vital signs/ECG is less important when there is at least 30 minutes between the placement of the catheter/blood sampling via catheter and vital signs/ECG.

Note 2: Predose assessments, including vital signs, ECG, physical examinations, and laboratory safety tests: within 3 hours predose.

The following collection time windows apply:

- Vital signs, ECG, and physical examinations: within 3 hours predose.
- Urine sampling: any time predose, on the same visit day.
- Blood sampling for clinical laboratory safety: within 3 hours predose.
- Blood sampling for PK:
 - Visit 1: predose (within 30 minutes prior to dosing) and at 0.5-1.5 hour, 2-2.5 hours, and 3-4 hours postdose.
 - Visit 3 and 4: predose (within 30 minutes prior to dosing)
 - Visit 5: predose (within 30 minutes prior to dosing) and 4-6 hours postdose
- [REDACTED]
- [REDACTED]
- [REDACTED]
- [REDACTED]
- Endoscopy and colon biopsy sampling:
 - At screening visit 2 (either surveillance colonoscopy or flexible sigmoidoscopy, see Section 8.7.2): once other in- and exclusion criteria have been confirmed at screening visit 1). The screening endoscopy should be completed prior to Day -8 (to allow results availability for Day 1), and between the endoscopy day (screening visit 2) and Day 1, there should be maximum 2 weeks.
 - At Visit 5 and ED visit, if applicable: can be on the day prior to, or on the day of the final IP dose.

When multiple assessments are listed on 1 line, the sequence can be determined by the site. Additional safety assessments should be performed if clinically indicated (see also Section 6.4).

8.1.1. Retesting During Screening

During the screening period, one retest of the following assessments is allowed:

- For resting pulse (after 5 min seated position) outside range for defining acute severe UC (as defined in exclusion criterion #18).
- For QuantiFERON –TB Gold test with indeterminate result (the subject is not eligible if retest result is indeterminate or positive).
- During screening or later during the study, retesting (resampling) of clinical laboratory safety tests or SARS-CoV-2 RT-PCR test is allowed once, only for technical or transport reasons (e.g., sample hemolyzed, out of stability, late arrival at laboratory impacting sample quality, loss, or destruction of the sample before analysis).

8.1.2. Rescreening of Subjects

If a subject is a screening failure, it is allowed to rescreen the subject once, if the reason for failure is temporary and expected to resolve, as judged by the investigator. When a subject is rescreened, the subject needs to be reconsented and all screening assessments need to be repeated. The subject will be assigned a new subject identification number. The time in between 2 screening attempts could vary depending on the screen failure reason.

The following data will be collected for screening failure subjects: ICF signed data, demographics, failed inclusion or exclusion criteria, and AEs.

8.2. Unscheduled Visits

Additional visits can be performed at other time points for any safety assessments, if clinically indicated. These unscheduled visits and outcomes of additional assessments need to be recorded in the source and, if it is a CSP-specified assessment performed before the subject's last visit per CSP, also in the eCRF.

8.3. Subject and Disease Characteristics

Subjects will be asked to attend the site for a screening assessment. After giving written informed consent, demographic data (year of birth, age, sex, ethnicity and race), medical, and smoking history will be taken, including UC history. UC classification and/or extent will be provided per

(see [Appendix 10](#)) based on the screening colonoscopy or endoscopy examination (where applicable, as per Section 8.7.2) or based on the last available colonoscopy performed before screening. Questions regarding prior and concomitant medication intake will be asked. A physical examination will be performed, including measurement of weight and height.

Vital signs (systolic and diastolic blood pressure, pulse, tympanic body temperature) will be measured and a triplicate 12-lead ECG will be recorded. Subjects should rest for at least

5 minutes, in the supine position before the ECG recording and in a seated position before blood pressure and pulse measurement. Blood and urine samples will be collected for clinical laboratory safety tests. A stool sample will be collected for microbiology and PD assessments. If not possible to collect a stool sample during the visit, the subjects will receive a stool sample collection kit to collect the stool sample at home within 24 hours after screening visit 1. A serum pregnancy test will be done for all WOCBP as well as an FSH test for nonsurgical postmenopausal female subjects.

UC history will capture the duration of disease, clinical symptoms, number of stools per day under normal (healthy/remission) conditions, medication used to treat the disease, and clinical response to current and prior UC therapies.

Flexible sigmoidoscopy or surveillance colonoscopy videos will be centrally reviewed using [REDACTED] and MCS-ES indices to confirm active UC. The endoscopy procedure will be done at a second screening visit after the other in- and exclusion criteria have been confirmed.

The inclusion and exclusion criteria (Sections 6.1 and 6.2) will be checked to assess eligibility for the study. All screening tests will be reviewed to confirm eligibility before randomization and the first dose.

8.4. Efficacy Assessments

8.4.1. Endoscopy

An endoscopy (either a surveillance colonoscopy or flexible sigmoidoscopy, see below) will be performed on the visits specified in the Schedule of Activities in Section 8.11 (see also Section 8.1, “[Timing of Assessments](#)”).

At screening visit 2:

- a. In subjects with a history of UC ≥ 8 years:
 - i) With a colonoscopy performed more than 24 months prior to screening, a surveillance colonoscopy will be performed.
 - ii) With a colonoscopy performed less than 24 months prior to screening, a flexible sigmoidoscopy will be performed.
- b. In subjects with a history of UC < 8 years:
 - i) A flexible sigmoidoscopy will be performed, irrespective of the time of the last colonoscopy.

At Visit 5 (or at the ED visit, if applicable):

- a. A flexible sigmoidoscopy will be performed for all subjects in the study.

Videos of the flexible sigmoidoscopy or of the screening surveillance colonoscopy, will be recorded. These will be reviewed and scored by blinded central reviewer(s) using the MCS-ES and [REDACTED] indices (refer to [Appendix 10](#) and [Appendix 11](#)). The MCS-ES (Schroeder,

Tremaine, & Ilstrup, 1987) [REDACTED] screening scores will be reported to the clinical site.

Details of the endoscopy, including bowel preparation before endoscopy, as well as the collection and processing of video films will be provided in a separate imaging charter.

8.4.2. Biopsy Sample Collection

During the endoscopy (either flexible sigmoidoscopy or surveillance colonoscopy) on the visits specified in the Schedule of Activities in Section 8.11 (see also Section 8.1, “[Timing of Assessments](#)”), 8 colonic biopsies will be collected per visit: 4 biopsies from the distal sigmoid colon (the area representative of UC disease activity) at approximately 25 cm proximal to the anal verge, and 4 biopsies from the rectum.

Colon biopsies will be stored at the site until shipment to a central lab for further processing, allowing:

- [REDACTED]
- [REDACTED]

Biopsy sample collection, handling, and processing will be outlined in the laboratory manual provided by the central laboratory.

8.5. Safety Assessments

This section describes methods and timing for all safety assessments and recording. Additional assessments (e.g. unscheduled clinical laboratory tests or extra vital signs recordings) are allowed to ensure appropriate collection of safety data and to assess any perceived safety concerns.

8.5.1. Adverse Events

Detailed definitions, reporting period, ratings and reporting requirements for AEs and SAEs are found in Section 11.

8.5.2. Clinical Laboratory Evaluations

The following clinical laboratory tests will be performed:

- **Hematology:** hematocrit, mean corpuscular volume (MCV), mean corpuscular hemoglobin (MCH), mean corpuscular hemoglobin concentration (MCHC), hemoglobin, red blood cell count, red blood cell distribution width, white blood cell count, white blood cell differential count (absolute and relative), platelets, and erythrocyte sedimentation rate (erythrocyte sedimentation rate at screening only).

– **Coagulation:**

INR (only when increase in LFTs, see Section 6.4), activated partial thromboplastin time, and prothrombin time.

– **Clinical chemistry:**

fasting glucose (at baseline [Visit 1], Day 15 [Visit 3], and Day 43 [Visit 5] and the ED visit, if applicable), glycosylated hemoglobin (HbA1c), fasting insulin (at baseline [Visit 1], Day 15 [Visit 3], and Day 43 [Visit 5] and the ED visit, if applicable), homeostatic model assessment of insulin resistance (HOMA IR) (at baseline [Visit 1], Day 15 [Visit 3], and Day 43 [Visit 5] and the ED visit, if applicable), urea, creatinine, creatinine clearance (ClCr), uric acid, sodium, potassium, calcium (total), reflex calcium (free/ionized; only if serum calcium total is elevated), chloride, phosphorus/phosphate, AST, ALT, GGT, total bilirubin, alkaline phosphatase (alkaline phosphatase bone fractions only if alkaline phosphatase is elevated), lactate dehydrogenase, creatine phosphokinase (CK), albumin, total proteins, triglycerides, total cholesterol, high density lipoprotein cholesterol, low density lipoprotein cholesterol, lipase, amylase, high sensitivity CRP, high sensitivity Troponin I and Troponin T (Troponin I on Day 1, later during the study only when troponin T is elevated).

Homeostatic model assessment of insulin resistance (HOMA-IR, see Definition of Terms) and HDL/LDL ratio will be derived from clinical chemistry parameters. An estimate of the creatinine clearance (ClCr) based on the serum creatinine level will be calculated by the central laboratory using the Cockcroft-Gault formula (see Definition of Terms).

– **Urinalysis:**

Dipstick: pH, glucose, proteins (qualitative), blood, leukocytes, ketones.

Microscopic examination of the sediment for cellular elements (cylinders, erythrocytes, leukocytes), if indicated (when the test strip was positive for blood and/or proteins).

Quantitative urine proteins, only when the test strip was positive for proteins.

Calcium, phosphate, creatinine and N-acetyl- β -D-glucosaminidase (NAG). The urine protein to creatinine ratio will be derived.

– **Serology/blood:**

HBs Ag, (if positive, confirmed by HBV DNA PCR), HCV (Ab and/or PCR) and HIV 1 and 2 antibodies (at screening). Positive hepatitis and HIV results should be reported by the investigator as required by local law.

FSH test for females of (nonsurgical) nonchildbearing potential at screening to confirm menopause, if applicable.

– **Pregnancy test for females:**

Serum beta human chorionic gonadotropin at screening, baseline (Visit 1), Day 29 (Visit 4), and Day 43 (Visit 5) or ED, if applicable (all female subjects).

– **QuantiFERON-TB Gold test** to check for latent or active TB (at screening). TB results should be reported by the investigator as required by local law.

– **Stool culture/ Stool sample for microbiology/microbiome evaluation:**

For enteric pathogens, *Clostridium difficile* cytotoxin assay and microscopic examination for intestinal parasites/ova in stool sample; *Escherichia coli*, *Salmonella* species (spp), *Shigella* spp, *Campylobacter* spp and *Yersinia* spp assay in stool culture (at screening).

Note: Details of microbiome assessment are provided in Section 8.7.3.2.

– **SARS-CoV-2:**

RT-PCR from a nasal swab sample to check for SARS-CoV-2 infection at screening and RT-PCR from a nasal swab sample and serology testing at baseline, and throughout the study as needed (when SARS-CoV-2 symptoms present)

The clinical laboratory evaluations will be performed at visits specified in the Schedule of Activities in Section 8.11 (see also Section 8.1, “[Timing of Assessments](#)”). Reference ranges will be supplied by the local and central laboratory, as needed.

Clinical laboratory values outside the normal range will be flagged and clinical relevance will be assessed by the investigator. Only laboratory test abnormalities judged as clinically significant by the principal investigator should be recorded as AEs. At the discretion of the investigator, when following up AEs, additional laboratory parameters may be tested, and additional samples taken.

In case of safety issues, as per decision of the investigator, the local laboratory at site could be used to verify some parameters.

An estimate of the ClCr based on the serum creatinine level will be calculated by the central laboratory using the Cockcroft-Gault formula (see [Definition of Terms](#)).

Blood, urine, and stool sample handling and shipment instructions will be provided in a separate laboratory manual.

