¹² On dosing days, safety urine samples will be taken predose, on the same visit day. Visit 1 and 5: predose and 2 hours postdose. Calcium and phosphate should only be evaluated at Visits 1 and 5.

¹³ At Screening Visit 1, a stool sample should be collected during the visit. If not possible, the subject can collect the sample at home within 24 hours after start of Screening. For Visits 1, 3, and 4, stool samples can be collected within 24 hours prior to the visit or during the visit. At Visit 5 (Day 43) and ED visit, if applicable, when the stool sample must be taken before the bowel preparation for endoscopy, stool can be collected more than 24 hours before the visit. One sample can be used for different assessments.

| EVENT | SCREENING PERIOD | | TREATMENT PERIOD ^{1, 2} | | | | | | FOLLOW-UP PERIOD ³ | | | | | | |
|---|----------------------|-----------------|--|-------|--------|--------|--------|-----------------|-------------------------------|--|--|--|--|--|--|
| | S1 | S2 ⁴ | 1 | 2 | 3 | 4 | 5 | ED ³ | | | | | | | |
| Study Visit | | | | | | | | | Follow-up Visit | | | | | | |
| Study Day (D) ± Days | -35 to 0 | | 1 | 8 ± 2 | 15 ± 2 | 29 ± 2 | 43 ± 2 | | 14± 3 after last IP dosing | | | | | | |
| • Microbiome (sampling before IP administration) (Section 8.7.3.2) | | | ✓ | | | | | ✓ | ✓ | | | | | | |
| Endoscopy + | | | | | | | | | | | | | | | |
| Mayo Clinical Score subscores (MCS-SF, MCS-RB, PGA) (Section 8.4.3) | | | ✓ | ✓ | | ✓ | ✓ | ✓ | | | | | | | |
| Subject diary evaluation (Section 8.8.1) | | | ✓ | ✓ | ✓ | ✓ | ✓ | ✓ | ✓ | | | | | | |
| Allocation and dispensing of IP supplies (Section 7.2) | | | ✓ | | ✓ | ✓ | | | | | | | | | |
| IP administration (Section 7.2) | | | Once daily throughout the treatment period ¹⁶ | | | | | | | | | | | | |
| Prior and concomitant medication (Section 6.3.2) | Throughout the study | | | | | | | | | | | | | | |
| Adverse events (Section 8.5.1) | Throughout the study | | | | | | | | | | | | | | |

¹⁴ Central endoscopy reading, [REDACTED]

¹⁵ Screening endoscopic assessment (either surveillance colonoscopy or flexible sigmoidoscopy) should be completed prior to Day -8.

¹⁶ On Visit 1, 3, 4, and 5, administration of IP must occur at the site.

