**Table 6: Analysis Visit Window for urine phosphate and urine calcium**

Visit date and time	Relative day (ADY)	Assessment visit (VISIT)	Time window (in ADY)*	Target day	Analysis visit (AVISIT)	Analysis time point (ATPT)
Before first study drug administration	<1 or pre-dose at ADY=1	Last assessment at any point in time before first study drug administration	<1 or pre-dose at ADY=1	1	Baseline	Pre-dose
Same as or after first study drug administration	$\geq 1$	Any scheduled (non follow-up), unscheduled, or early discontinuation visit	1	1	Day 1	2 hours post-dose
			13 to 22	15	Week 2	
			23 to 36	29	Week 4	
			37 to 49	43	Week 6	As indicated in the database: Pre-dose and 2 hours post-dose
		Follow-up	CRF collected follow-up visit		Follow-up	

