#### 4.3.5. Selection and Use of Analysis Visits

Before first administration of IP, only Baseline will be used for the entire statistical analysis. Pre-baseline assessments will only be listed. After first administration of IP, if multiple valid, non-missing assessments exist in an analysis window, records will be chosen based on the following rules if a single value is needed:

- The record closest to the nominal day for that visit will be selected, or
- If there are 2 records that are equidistant from the nominal day, or more than 1 record (with time known) on the selected day, the latest record will be taken
- If chronological order cannot be determined (e.g., more than 1 record on the same day with time missing), the average of the records will be computed and reported in the analysis

For the [REDACTED] endpoints including MCS, [REDACTED], the following steps will be used to derive each composite endpoint, unless otherwise specified:

- Step 1: Put [REDACTED] component value into an analysis visit window.
- Step 2: Within each visit window, select the data points for analysis.
- Step 3: Combine these selected data points within each analysis visit window across the components.

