#### **6.3.2.2. Derivation Rules**

##### **Derived Laboratory Tests**

Not applicable.

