### 6.3.2.9. Presentation of Results

No formal inferential statistics (p-values) will be derived.

Continuous laboratory tests including glucose, cholesterol, triglycerides, low-density lipoprotein (LDL), high-density lipoprotein (HDL) and fasted glucose will be summarized by means of descriptive statistics (including 90% CI of the mean change) by laboratory test, treatment group and analysis window. Actual values, changes from baseline and percent change from baseline will be tabulated separately. Continuous values for metabolic markers will be summarized in the PD analysis section ([section 6.5](#)).

Profile line plots by subject of all actual observed values using relative day (ADY) will be presented by treatment group. Graphs of the mean (+- SE) actual values over time and of the mean (+- SE) change from baseline, and percent changes from baseline will be presented for all continuous laboratory parameters, with the exception of the metabolic markers. Also, line plots for subjects will be provided by treatment group.

The analysis of abnormalities will focus on assessments reported during the treatment period. Results reported before baseline will only be listed.

Non-graded abnormalities and toxicities grades of the actual values will be presented as shift tables of the worst-case abnormality/toxicity grade versus the baseline abnormality/toxicity

---

 With the exception of the metabolic markers [fasted insulin, homeostatic model assessment of insulin resistance (HOMA-IR) and HbA1c] and other markers hsCRP and fecal calprotectin .

grade. The table will be created per laboratory test, treatment group and analysis period. The results of non-graded abnormalities and toxicities grades will be shown separately.

A frequency table of the number (percent) of subjects with treatment-emergent worst-case abnormalities/toxicity grade per laboratory test, treatment group and analysis period will be presented. The results of non-graded abnormalities and toxicities grades will be shown separately.

A frequency table of the number (percent) of subjects will be also provided for the hepatotoxicity flags defined before. These abnormalities will be also flagged in the individual data laboratory listing.

Listing will be provided for the laboratory test along with flag for abnormality results. In addition, pregnancy result will be listed separately.

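### Urine NAG, calcium and phosphate are summarised without indexing to urine creatinine, although creatinine is on the same urine panel; variation in urine concentration adds avoidable noise

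*Protocol*

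**What the plan says.** Protocol 8.5.2 lists, under urinalysis, "Calcium, phosphate, creatinine and N-acetyl"-β-D-glucosaminidase (NAG), and then states: "The urine protein to creatinine ratio will be derived". No other urine ratio is named. Quantitative urine protein is measured only when the test strip is positive.

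Protocol 8.1 allows urine to be taken at any time predose on the visit day. Footnote 12 of the Schedule of Activities (Protocol 8.11) adds, for safety urine: "Visit 1 and 5: predose and 2 hours postdose. Calcium and phosphate should only be evaluated at Visits 1 and 5".

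In SAP 6.3.2.2, the entry under "Derived Laboratory Tests" is that none apply. SAP 6.3.2.9 says of continuous laboratory tests: "Actual values, changes from baseline and percent change from baseline will be tabulated separately", with a 90% CI of the mean change, profile plots by subject and shift tables. Footnote 17 excepts fasted insulin, HOMA-IR, HbA1c and "other markers hsCRP and fecal calprotectin"; no urine analyte is on that list.

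SAP Table 6 is headed "Analysis Visit Window for urine phosphate and urine calcium" and keeps predose and 2 h postdose values apart for those two tests. All other non-PK assessments fall under Table 3. Where several records lie in one window and a single value is needed, SAP 4.3.5 provides that if there is "more than 1 record (with time known) on the selected day, the latest record will be taken".

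**The concern.** The concentration of a solute in an untimed urine sample depends on how dilute the urine is as well as on how much is excreted. Dividing by creatinine from the same sample is the usual way to remove much of the first component, and the protocol accepts that logic for protein. Leaving it out for NAG, calcium and phosphate means that a rise in excretion can be obscured when the later sample is dilute, and an apparent rise can appear when it is concentrated. Appendix I of the SAP gives no toxicity grades for these three urine tests, so the summaries of change, the subject plots and any normal-range shift tables are their only visible read-outs. With 20 and 10 subjects planned, added noise matters.

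A second issue depends on what is assayed at 2 h. If NAG or creatinine is tested on that sample, the general window rules would pair unlike time points at Week 6.

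**Working it through.** **Document check**

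1. Is indexing planned? Protocol 8.5.2 plans it for protein only. SAP 6.3.2.2 plans none, Table 6 handles urine calcium and phosphate under their own names, and footnote 17 of SAP 6.3.2.9 does not take any urine test out of the general summaries. The visible text of SAP 6.6 (changes from the protocol) does not mention the protein/creatinine ratio, although Protocol section 9 asks for deviations to be justified in the SAP.
2. Are like time points compared?
   - *Calcium and phosphate:* yes. Table 6 has a predose baseline and separate predose and 2 h values at Week 6.
   - *NAG and creatinine, if assayed at 2 h:* no. Table 3 makes the last value before first dose the baseline. With two timed records on Day 43, SAP 4.3.5 picks the later, 2 h postdose one. The post-dose windows of Table 3 start after relative day 1, so a Day 1 2 h value has no window and cannot serve as the comparator.

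**Size**

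The documents state no figure for these tests, so there is nothing to reproduce, and they give no variances. The following is an illustration.

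*Assumptions:* on the log scale, raw concentration = creatinine-indexed value + dilution. The two parts are independent of each other and between visits, creatinine removes all of the dilution part, and each part has a within-subject CV between 20% and 70%. Arm sizes of 20 and 10 are from Protocol 5.1.

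*Formulas:* v_d = ln(1 + CV_d²) for dilution and v_a = ln(1 + CV_a²) for the indexed analyte.

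- Share of the variance of the raw log change due to dilution = v_d / (v_d + v_a).
- Between-arm 90% CI factor = exp(1.645 × √[2v(1/20 + 1/10)]), with v = v_d + v_a for raw values and v = v_a for the ratio.

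*Example, CV_d 50%, CV_a 30%:* v_d = ln 1.25 = 0.2231 and v_a = ln 1.09 = 0.0862. The share is 0.2231/0.3093 = 72%. The raw SE is √(0.30 × 0.3093) = 0.305, factor 1.65. The indexed SE is √(0.30 × 0.0862) = 0.161, factor 1.30.

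| CV dilution | CV analyte | Dilution share | 90% CI factor, raw | 90% CI factor, ratio |
|---|---|---|---|---|
| 20% | 70% | 9% | 1.82 | 1.77 |
| 20% | 50% | 15% | 1.59 | 1.53 |
| 50% | 50% | 50% | 1.83 | 1.53 |
| 50% | 30% | 72% | 1.65 | 1.30 |
| 70% | 20% | 91% | 1.82 | 1.20 |

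The SAP plans a CI of the mean change within each arm, not between arms. For the 50%/30% example on the log scale, SE = √(2v/n):

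- *n = 20:* 0.1759 raw against 0.0928 indexed, factors 1.34 and 1.16.
- *n = 10:* 0.2487 raw against 0.1313 indexed, factors 1.51 and 1.24.

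Using t quantiles instead of 1.645 would widen all of these somewhat.

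**The case against.** **Dilution dominates the changes.** A reader might infer this, but the documents do not support it. The share exceeds one half only where dilution varies more than the indexed analyte does, and neither variance is given.

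**The treatment comparison is biased.** This does not follow either. Both arms are randomised and both drink a reconstituted oral solution (Protocol 7.2), so fasting and fluid intake affect them alike. Unless the drug alters urine volume, dilution is noise between arms. That answer is only partial, because SAP 6.3 plans no formal comparison of arms on safety data and the planned outputs are within arm and within subject.

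**The entry in SAP 6.3.2.2 proves that the protein ratio was dropped.** That over-reads it. The protocol also says HOMA-IR will be derived, yet the SAP deals with it elsewhere (footnote 17 and section 6.5) under the same not-applicable entry. SAP section 1 places technical details of derivations in a separate document, section 6.5 is not visible, and the laboratory's reporting units are not stated. That the values are raw concentrations is therefore an inference from silence. What stands is that no visible text plans the ratios.

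**NAG at Week 6 is compared across different times after dosing.** This is conditional. Footnote 12 can be read as a full second safety sample, or as one meant for calcium and phosphate, which the title of Table 6 would fit.

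**The stakes are limited.** This stands. Serum creatinine, creatinine clearance, urea, calcium and phosphate are also measured, and no endpoint or visible decision rule rests on these urine tests.

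**Conclusion.** The visible plan summarises urine NAG, calcium and phosphate from untimed single samples without indexing to a creatinine value on the same panel, and the protocol's protein/creatinine ratio does not reappear in SAP 6.3.2.2. The likely consequence is avoidable noise in within-arm changes, subject profiles and, where the laboratory supplies normal-range flags, shift tables. Under the assumed CVs of 20% to 70%, dilution contributes 9% to 91% of the variance of the log change, so the gain from indexing ranges from slight to large. These figures also assume that creatinine corrects dilution fully and that visits are independent; within-subject correlation would reduce the raw figures. The mismatch of time points is a real defect only if NAG or creatinine is assayed at 2 h postdose. The point is a low-cost improvement to descriptive safety summaries and has no bearing on the primary Mayo score analysis.

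**What to change.** 1. In SAP 6.3.2.2, replace the not-applicable entry with these derived tests: NAG/creatinine, calcium/creatinine and phosphate/creatinine for each urine sample in which both quantities are assayed (calcium and phosphate at Visits 1 and 5 only), and protein/creatinine where quantitative protein was measured.
2. In SAP 6.3.2.9, summarise change from baseline in these ratios by arm, preferably on the log scale, beside the raw values.
3. State which urine tests are run on the 2 h postdose samples at Visits 1 and 5. If NAG or creatinine is among them, extend Table 6 to those tests so that predose is compared with predose and 2 h with 2 h.
4. If the separate derivations document or section 6.5 already covers the ratios, a cross-reference in 6.3.2.2 is enough.

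The cost is a short SAP edit and a few lines of programming. Because the ratios are limited to samples in which both quantities are assayed, no new samples or assays are needed.
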